- 2) Newly diagnosed chronic phase (CP)-CML patients planned to receive one of the three TKI approved as first line treatment (i.e., imatinib, dasatinib or nilotinib);
- 3) Adult patients (≥ 18 years) at the time of study entry; Children under the age of 18 will be excluded from the study. The exclusion of children is justified by the following circumstances: a) The condition is relatively rare in children, as compared to adults; b) Issues of study preclude direct applicability of hypotheses and/or interventions to both adults and children.
- 4) Written informed consent.
- 5) Written informed consent from patient’s physician as a participant.

- 5) Newly diagnosed chronic phase (CP)-CML patients who are within 4 weeks of first line TKI therapy (any of the three TKI approved in the USA and Europe, that is: imatinib, dasatinib or nilotinib).
- 6) Ability to read/converse in English (Northwestern University and Augusta University sites). Ability to read/converse in Italian (GIMEMA site).

Patient exclusion criteria will include:

- 1) Major cognitive deficits or psychiatric problems hampering a self-reported evaluation;
- 2) Having received any CML treatment prior to therapy with imatinib, dasatinib or nilotinib for more than three months.

This project will focus on CML, which affect both men and women. Therefore, there are no exclusion/inclusion criteria based on sex/gender. In addition, there are no exclusion/inclusion criteria based on race and ethnicity.

Physician inclusion criteria will include:

- 1) Provider of clinical care for patient who meets inclusion criteria for the study

Please note that physician consent is requisite for the patient to be enrolled as a participant in the study.

4.0 Sample Size:

Sample size is based on the available resources for conducting this study. We define the adherence rate (AR) as the overall proportion of pills taken out of those prescribed, from baseline to six months, averaged over the number of pill-count assessments. Based on adherence rates reported by previous works^{10,18}, we defined 72% as a minimum threshold of AR (H0). In order to detect at least 85% of AR (H1), with power of 80% and 2.5% type I error probability (one sided exact test for binomial proportions), we will need 84 patients. However, considering overall 11% of attrition rate, 94 patients are actually required.

5.0 Recruitment and Screening Methods:

Each study site will follow the same recruitment and screening methods.

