Based on H0 and H1, power and Type I error ($\alpha=0.025$) as specified in the section “Sample size”, we define the intervention achieving an *optimal adherence rate* if at least 82% of patients (n=69/84) will take at least 90% of prescribed drug (Marin D, Bazeos A, Mahon FX, et al. J Clin Oncol. May 10 2010). We define adherence as *acceptable* if at least 72% of patients (n=61/84) take at least 90% of prescribed drug. Thus, we will consider 82% and 72% as thresholds defining respectively *optimal* and *acceptable* adherence rates based on the actual number of enrolled patients. Proportions of TKI responses at three and at six months and time to achieve treatment milestones will be reported. We will estimate HRQoL and fatigue outcomes trajectories over time by a repeated measure linear mixed model, assessing possible changes from baseline by an overall F-test testing the null hypothesis of no difference. Reasons for missing PRO collection at follow-up visits will be collected as well. Based on similar studies (Basch E, Iasonos A, Barz A, et al. J Clin Oncol. Dec 01 2007; 25(34):5374-5380) the intervention will be considered feasible if at least 80% of participants complete online questionnaires at more than 60% of follow-up visits (i.e., after initial visit up to six months). We will describe all outcomes regarding feasibility, patient and physician acceptability by absolute frequencies and proportions. In addition, we will use the generalized linear mixed model (GLMM) to investigate about possible determinants of single relevant aspects (items) of acceptability, both for patients and physicians. Using the same GLMM approach, we will estimate the impact of the initial TKI on the adherence rate, accounting

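### The fixed 82% cut for 'optimal' adherence does not follow the plan's own exact test at every enrolled number, and the lower label 'acceptable' starts at the null value without an interval.

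*Combined protocol and SAP*

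**What the plan says.** Section 4.0 (Sample Size) fixes the hypotheses: "we defined 72% as a minimum threshold of AR (H0"). The alternative is 85%, and the design is set "with power of 80% and 2.5% type I error probability (one sided exact test for binomial proportions"). It arrives at 84 patients and then inflates for loss: "considering overall 11% of attrition rate, 94 patients are actually required".

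Section 9.0 (Data analysis plan, Primary analysis) ties these hypotheses, the power and the alpha of 0.025 to the label *optimal*. That label is reached when at least 82% of patients, 69 of 84, take at least 90% of the prescribed drug. A separate sentence gives a second favourable label: adherence is *acceptable* "if at least 72% of patients (n=61/84) take at least 90% of prescribed drug". Both percentages are then generalised: "we will consider 82% and 72% as thresholds defining respectively" *optimal* and *acceptable* "adherence rates based on the actual number of enrolled patients".

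The same paragraph says of other endpoints: "We will describe all outcomes regarding feasibility, patient and physician acceptability by absolute frequencies and proportions". Adherence is not in that list, and the text available for review plans no confidence interval for the adherence proportion.

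**The concern.** There are two issues, both about how the primary result is classified.

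1. **The upper cut.** The 82% figure is the critical value of an exact test at n = 84, expressed as a percentage. Exact critical values move in whole patients and not in proportion to n. A percentage that is right at 84 can therefore be one patient off at another n, including the 94 that the plan intends to enrol. The trial could then miss its own success criterion on data that reject H0 or, less likely, meet it on data that do not.

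2. **The lower cut.** The label *acceptable* begins at the null value. A count from 61 to 68 of 84 would be reported under a favourable name, with no statement that H0 stands and no interval to show how far below 72% the true rate could lie. The study is meant to inform a later randomised trial, so the reading of such a middling result matters.

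**Working it through.** **Inputs.** p0 = 0.72, p1 = 0.85, one-sided alpha 0.025, power 80%, exact binomial test, n = 84 and enrolment 94 (Section 4.0). Cuts of 82% (69/84) and 72% (61/84), applied to the number enrolled (Section 9.0). The 72% is read as a proportion of patients; see the verdict.

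**Formulas.** With X ~ Bin(n, p): alpha(r) = P(X ≥ r | 0.72) and power(r) = P(X ≥ r | 0.85). The exact critical value is the smallest r with alpha(r) ≤ 0.025. The literal cut is the smallest whole number at or above 0.82n. Intervals are Clopper–Pearson, two-sided 95%.

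**Step 1: the plan's own figure.** At n = 84, 0.82 × 84 = 68.88, so the literal cut is 69. Alpha(69) = 0.0221 and power(69) = 0.8146, while alpha(68) = 0.0403. The exact critical value is 69, so the stated design and cut reproduce.

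**Step 2: carry 82% to other n.** For n = 78 to 94 the two cuts differ at five values:

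| n | 0.82n | literal cut (alpha, power) | exact cut (alpha, power) |
|---|---|---|---|
| 78 | 63.96 | 64 (0.0282, 0.8151) | 65 (0.0144, 0.7243) |
| 88 | 72.16 | 73 (0.0121, 0.7596) | 72 (0.0232, 0.8384) |
| 92 | 75.44 | 76 (0.0129, 0.7886) | 75 (0.0242, 0.8593) |
| 93 | 76.26 | 77 (0.0111, 0.7752) | 76 (0.0210, 0.8487) |
| 94 | 77.08 | 78 (0.0095, 0.7614) | 77 (0.0182, 0.8376) |

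At 79–87 and 89–91 they agree. At the planned 94, a count of 77 (77/94 = 81.9%) rejects H0 but falls short of 82%, so it would be labelled only *acceptable*. The literal cut costs 83.8 − 76.1 = 7.7 percentage points of power there.

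**Step 3: the lower label at n = 84.** 0.72 × 84 = 60.48, so the cut is 61 (60/84 = 71.4%; 61/84 = 72.6%).

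| count | one-sided p against 72% | exact 95% CI |
|---|---|---|
| 61/84 | 0.505 | 61.8–81.8% |
| 68/84 | 0.040 | 70.9–88.7% |
| 69/84 | 0.022 | lower limit 72.3% |

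No count from 61 to 68 rejects H0; 69 is the first whose interval excludes 72%. The chance of landing in the 61–68 band is 48.3% at a true rate of 72%, 59.1% at 80% and 18.4% at 85%, so it is not a remote outcome.

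**The case against.** **The labels form a coherent scale.** The alpha clause belongs to *optimal* alone, and Section 4.0 calls 72% a minimum. *Acceptable* can therefore mean that the observed rate is not below that minimum, with *optimal* reserved for rejection of H0. This stands. What is left is that the plan does not say so and gives no interval.

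**About half of trials at a true 72% would earn the lower label.** The probability is 50.5%, and a reader might infer a 50% type I error. The documents do not support that: no test or error rate is attached to *acceptable*, and any cut placed at the null value is met about half the time when the null is true. The label still separates clearly poor adherence, since the chance of 61 or more is 8.7% at a true rate of 65% and 1.1% at 60%.

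**The literal 82% is mostly conservative.** This is true. Within 78 to 94 it exceeds 2.5% only at 78; elsewhere a mismatch costs power and not type I error. But the loss falls at the planned enrolment and takes power below the stated 80%.

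**Perhaps 82% is a rounded figure.** A reader might then let 77/94 qualify, or argue that alpha is exceeded at other n where a count rounds to 82%. The plan says at least 82% and gives no rounding rule, so neither argument has support in the text.

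**It is a pilot, and the count will be visible.** No decision about the later trial is made to depend on *acceptable*, and a reader could compute the interval. This is why the point is minor.

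**Conclusion.** The point holds in two limited parts.

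- A fixed 82% is not equivalent to the plan's exact test at every n. At the planned 94 it is one patient too strict: 78 instead of 77, power 76.1% instead of 83.8%. At 78 it is one too lenient, with alpha 2.8%.
- *Acceptable* starts at the null, and 61 to 68 of 84 would be named favourably although rates below 72% are not excluded. The plan does not state this and, in the text available, provides no interval.

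The sample size, the test and the 69/84 cut at n = 84 are sound. Severity is minor.

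Assumptions:

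- 82% is read literally.
- 72% is a proportion of patients, as Section 9.0 and a binomial test require. Section 4.0 words the rate as "the overall proportion of pills taken out of those prescribed", which is a separate inconsistency.
- The figures at 94 suppose that all 94 can be classified, with a common success probability. The plan does not say how dropouts count in the enrolled denominator; 94 × 0.89 = 83.66 would remain after the planned attrition.

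**What to change.** 1. Define *optimal* (exceeds 72%) as rejection by the one-sided 2.5% exact binomial test at the actual number in the denominator the plan names, in place of a fixed 82%. This gives 69/84, or 77/94 if 94 are enrolled.
2. State that *acceptable* describes an observed rate at or above 72% and does not reject H0.
3. Report the adherence proportion with its exact two-sided 95% CI, whichever label applies.

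Keep the enrolled denominator unless it is changed openly. A move to an analysed denominator is a separate question about how dropouts count, and should be flagged as such.

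The cost is SAP wording and one interval, with no change to the sample size. The cut may move by one patient at some n. Power is lost only where the literal cut was too lenient: at 78, from 81.5% to 72.4%. The exact rule does not itself guarantee 80% power at every n (74.3% at 83, where both cuts are 69). The weaker label would carry a qualification, which at n = 84 affects 59% of trials if the true rate is 80% and 18% if it is 85%.

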facilitate medication-taking behaviors (possibly from the very beginning of therapy), to boost drug effectiveness and maximize chance to obtain optimal long-term outcomes. Despite compelling evidence of the need to improve adherence to TKI therapy in order to improve clinical outcomes in CML¹⁰⁻¹², intervention studies aimed at this goal are lacking¹³. Our proposed study is innovative in the following ways: 1) it will assemble a comprehensive list of symptomatic AEs relevant for the CML population under TKI therapy; 2) it will develop an online platform specifically devised to monitor patient-reported AEs in CML; 3) it may establish a new model for routine CML care that could increase treatment-free remissions (TFRs). Finally, a major innovation of this proposal is its international element, across Italy and the United States, allowing us a window to explore cultural variation in response to the intervention.

In this regard, another major point of innovation of our proposed research is the potential to establish a new model of routine CML care that could maximize clinical response (by increasing adherence to therapy) and eventually offer the possibility to stop lifelong TKI treatment to a greater proportion of CML patients. Also, considering, the high costs of TKI therapies, which currently impose a substantial financial burden to many CML patients and healthcare systems¹⁴, any research effort aimed at maximizing chances to TFR, such as the one proposed in this application, may have major implications in reducing healthcare costs.

Ultimately, according to previous findings showing that an ‘integrated’ patient-centered approach of PRO evaluation in clinical practice is feasible and associated with a number of benefits¹⁵⁻¹⁷, we plan to conduct a large international RCT to investigate whether prospective and systematic electronic PROs collection in newly diagnosed CML patients improves clinical response to therapy and long-term patient outcomes.

The intervention that will be piloted is the real-time collection of patient-reported AEs during clinical visits, with real-time feedback to treating physicians who will then have this data available, already at the time of consultation.

3.0 Inclusion and Exclusion Criteria:

Patient inclusion criteria will include:

- 1) Diagnosis of Philadelphia chromosome positive and/or BCR-ABL positive CML confirmed by cytogenetic and/or molecular analysis;

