The sources of research material obtained from participants will be the participants themselves in the form of medical history and patient-reported data. Participants will furnish demographic and psychosocial information and patient-reported outcomes. We will also collect medical treatment and disease characteristics (e.g., type of treatment, time since diagnosis, etc.). Medical treatment and disease characteristic information will be collected via chart review by our research team under procedures established in prior work. All material will be obtained exclusively for research purposes and in full IRB and HIPAA compliance. All sources of information will be coded using a special participant number, which precludes it being matched with identifying information. Because all our participants will be individuals treated for CML, the issues surrounding confidentiality are of supreme importance. The participants will sign a statement attesting to their understanding that the information they provide will be held as personal and confidential to the extent permitted by law. Access to the computer data files will be by password codes. The list matching participant number to identifying information will be maintained in a locked drawer in the office of the PI. Additionally, in order to be able to track participants across the longitudinal period of the project, we will keep a separate record of each participant's address, telephone number and contact person information. This record will indicate whether or not a participant has completed an assessment but will not include information concerning their assessment or intervention performance. Participants will be made explicitly aware at the time of the informed consent of the nature of the two separate records that will be kept.

Patient assessment and report program will be loaded into tablets for electronic administration in the clinic setting. The **CHES** platform enables this administration with an already existing web-based software. Therefore, the **CHES** web-based platform, will

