for the different subject-specific number of pill count assessments over time and for the within-subject correlation of measurements. Successful management of emergent adverse events caused by the initial TKI does include the option of switching to a different TKI and we will not consider this as adherence failure. That is, we will measure adherence primarily as the composite use of all TKI agents. However, we will investigate the impact of these changes on the outcomes of interest via sensitivity analyses. We will assess the potential impact of initial TKI on different outcomes including this information as a covariate in all corresponding analyses. Unless not differently specified above, all the statistical tests will be two-sided with statistical significance set as $p < 0.05$.

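### The plan estimates an impact of the non-randomised initial TKI on adherence with no confounder named, and no model names country or site

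*Combined protocol and SAP*

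**What the plan says.** Section 3.0 admits newly diagnosed patients who are planned for imatinib, dasatinib or nilotinib, or are within four weeks of such therapy. The documents describe no random allocation to TKI.

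In section 9.0 (Data analysis plan, Primary analysis) the plan says "we will estimate the impact of the initial TKI on the adherence rate" by GLMM, accounting "for the different subject-specific number of pill count assessments over time and for the within-subject correlation of measurements". The idea is then extended to the other endpoints: "We will assess the potential impact of initial TKI on different outcomes including this information as a covariate in all corresponding analyses". Switches of TKI are handled by sensitivity analyses. Initial TKI is the only covariate named in the analysis plan. A separate GLMM looks for determinants of acceptability but does not list them.

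Section 2.0 calls the international element a major innovation, "allowing us a window to explore cultural variation in response to the intervention". No model or summary in the analysis plan names country or site.

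Data for adjustment will exist. Section 6.0 (Procedures for data collection and safeguard) says "Participants will furnish demographic and psychosocial information and patient-reported outcomes" and adds that treatment and disease characteristics come from chart review.

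**The concern.** The number of pill counts and the within-patient correlation are features of repeated measurement. Handling them gives sound standard errors but does not make the TKI groups comparable. The switching sensitivity analyses concern what happens after baseline, not how the initial groups arose. A patient's first TKI may depend on country, age, sex or disease features, and any of these may also be related to adherence. The plan would then report a difference in patient mix or country as an impact of the drug, tested two-sided at 0.05.

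Country matters in a second way. The protocol offers the two-country setting as a feature worth exploring, but no planned estimate describes adherence, feasibility or quality of life by country.

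**Working it through.** **The plan's own figure.** The TKI comparison has no stated size or power. The only design figure is for the primary single-arm test: "In order to detect at least 85% of AR (H1), with power of 80% and 2.5% type I error probability", with a "one sided exact test for binomial proportions" and a null value of 72%. For the rule of at least 69 of 84, the exact binomial tail is 0.0221 at 0.72 and 0.8146 at 0.85, so 84 reproduces. For 11% attrition, 84/0.89 = 94.4 (95 rounded up) and 84 × 1.11 = 93.2 (94 rounded up), so the stated 94 is within one patient. This design compares one proportion with a fixed value and does not involve TKI or country.

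**Illustration of confounding by country.** Every input in this step is an assumption, because the documents give no split by TKI or country: two countries of equal size, two drug groups, no true drug effect, and one 90%-adherent yes/no outcome per patient. Let drug A be used by a share *a* of patients in country 1 and *b* in country 2, with *a* + *b* = 1. Country 1 then makes up a share *a* of the drug A group and *b* of the drug B group, so

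spurious drug difference = (*a* − *b*) × (country difference in adherence).

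For a 10-point country difference:
- 50/50: (0.5 − 0.5) × 10 = 0 points
- 70/30: (0.7 − 0.3) × 10 = 4 points
- 90/10: (0.9 − 0.1) × 10 = 8 points

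For a 13-point difference (0.85 against 0.72, the plan's H1 and H0 borrowed only as a range), with 84 patients in two drug groups of 42, the chance of p < 0.05 is Φ(d/SE − 1.96) + Φ(−d/SE − 1.96), where SE² = pA(1 − pA)/42 + pB(1 − pB)/42.

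| Drug A use, country 1 / country 2 | pA, pB | Spurious difference (points) | Odds ratio | Chance of p < 0.05 |
|---|---|---|---|---|
| 50/50 | 0.785, 0.785 | 0 | 1.00 | 5% |
| 60/40 | 0.798, 0.772 | 2.6 | 1.17 | 6% |
| 70/30 | 0.811, 0.759 | 5.2 | 1.36 | 9% |
| 80/20 | 0.824, 0.746 | 7.8 | 1.59 | 14% |
| 90/10 | 0.837, 0.733 | 10.4 | 1.87 | 22% |

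A country term removes this bias in the illustration, because adherence is the same for both drugs within each country.

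**Precision.** With 84 patients spread evenly over three TKIs (28 each), power to separate 0.72 from 0.85 between two TKIs is about 22%; 80% would need 156 per group. At about 78% adherent, the 95% half-width for a difference is 1.96 × √(2 × 0.78 × 0.22/28) = 0.22, or about 22 points. For two groups of 42 it is about 18 points.

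**Room for covariates.** If 72% to 85% are adherent, 84 patients give 84 × 0.15 = 12.6 to 84 × 0.28 = 23.5 non-adherent patients. TKI (2 parameters), country, age and sex make 5, or about 2.5 to 4.7 non-adherent patients per parameter if the outcome is dichotomised.

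**The case against.** The strongest reply is that this is a secondary analysis in a single-arm pilot and that imprecision dominates. A 4-point bias is small beside a half-width of 18 to 22 points, and adjustment does not narrow the interval. Cultural variation appears only in the background; it is not a specific aim, a listed outcome or a basis for the sample size. The open list of determinants in the acceptability GLMM could include country, so the exact statement is that no model names it. All of this stands. It limits the weight of the point but does not remove it: wide intervals do not justify the word *impact*, and the changes are cheap.

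A second objection concerns the choice of covariates. Section 3.0 admits patients within four weeks of first-line therapy, so baseline FACT-G may be measured after the drug has begun. The protocol's rationale is that TKI side effects lower quality of life and drive non-adherence. FACT-G could then lie on the path from drug to adherence, and adjusting for it could remove a real effect. This objection stands and shapes the fix.

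A reader might also infer three stronger things that the documents do not support:
- *That the TKI estimate is certainly biased.* Bias needs both TKI use and adherence to differ by country or patient mix. The documents give neither, and equal TKI use gives zero bias from country.
- *That drug, patient and country effects cannot be separated.* The plan as written does not separate them, but demographic, treatment and disease data are collected and country is known from the recruiting site.
- *That the result could steer TKI selection in the later RCT.* That trial is to test electronic collection of patient-reported outcomes, and nothing ties TKI stratification or selection to this estimate.

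**Conclusion.** The point holds in a limited form. Initial TKI is not randomised, the adherence GLMM names no confounder, and no model names country or site. Followed as written, the plan would report a possibly confounded contrast as an impact and would leave the two-country interest without an estimate.

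The possible bias is conditional and its size is unknown. In the illustrations it runs from 0 with equal TKI use to 4 points (70/30) or 8 points (90/10) for a 10-point country difference, and to 10.4 points in the most extreme case tabulated. For scale, the plan's acceptable and optimal thresholds, 72% and 82%, are 10 points apart. The figures rest on assumed splits, two drug groups and a yes/no outcome; they show the mechanism and do not forecast the result. The primary adherence threshold and the sample size are not affected.

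**What to change.** In the analysis plan:

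1. Add country, age and sex as fixed effects to the TKI adherence GLMM. Use country rather than individual centre, because the Italian network has about 150 centres.
2. Add country to the HRQoL and fatigue mixed models.
3. Use baseline FACT-G as an adjuster only where it was measured before the first TKI dose.
4. Call the TKI result an exploratory adjusted association, and state that residual confounding remains, since a short covariate list cannot capture all the reasons for the choice of drug.
5. Report adherence and feasibility proportions by country with exact confidence intervals. With no control arm, these describe outcomes under the intervention in each country, not a difference caused by it.

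The cost is wording, three extra parameters in the adherence model and one in each HRQoL or fatigue model. No new data are needed. The downside is that, with about 84 to 94 patients and few non-adherent ones, the adjusted estimates and by-country intervals will be wide.
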